#### **4.2.9.2 Laboratory data**

All continuous laboratory parameters will be summarized descriptively by absolute value at each visit by treatment group, together with the corresponding changes from baseline. All parameters will be summarized in SI units, with the exception of blood eosinophil counts which will be summarized in both SI and conventional units. Results which are reported from the central laboratory in conventional units will be converted to SI units for reporting.

Central laboratory reference ranges will be used for the identification of abnormalities, and a shift table will be produced for each laboratory parameter to display low, normal, high values, and missing values. The shift tables will present baseline and post-baseline maximum/minimum value, as applicable, for each parameter and will include patients with both baseline and post-baseline data.

Shift plots showing each individual patient's laboratory value at baseline and at maximum/minimum post-baseline will be produced for each continuous laboratory variable. If any laboratory variables show any unusual features (high or low values or a general shift in the data points) at other timepoints, then shift plots of these data may be produced.

Data for patients who have treatment-emergent changes outside central laboratory reference ranges will be presented. This data presentation will include all visits for this subset of patients.

Maximum post-baseline bilirubin elevations by maximum post-baseline ALT and AST will be presented, expressed as multiples of ULN. Bilirubin will be presented in multiples of the following ULN:  $\leq 1.5$ ,  $>1.5-2$ , and  $>2$ . Alanine aminotransferase and AST will be presented in multiples of the following ULN:  $\leq 1$ ,  $>1-3$ ,  $>3-5$ ,  $>5-10$ , and  $>10$ .

Maximum post-baseline total bilirubin (TBL) will be presented ( $<2$  and  $\geq 2xULN$ ) and plotted against maximum post-baseline ALT ( $<3$ ,  $\geq 3- <5$ ,  $\geq 5- <10$ , and  $\geq 10 x ULN$ ), expressed as multiples of ULN. This will be repeated to show maximum post-baseline TBL against maximum post-baseline AST.

Data for patients with ALT or AST  $\geq 3xULN$ , and TBL  $\geq 2xULN$  will be presented, which will include all visits for this subset of patients. A line plot of liver biochemistry test results (including ALP, ALT, AST, TBL, and GGT) over time will also be presented for this subset of patients.

For urinalysis data, a shift table will be generated to present changes from baseline to maximum post-baseline value for each parameter and will include patients with both baseline and post-baseline data.

Descriptive statistics will be presented for IgE baseline value by treatment group.

Any data outside the central laboratory reference ranges will be explicitly noted on the listings that are produced.

#### **4.2.9.3 Electrocardiograms**

A shift table will be produced for each ECG parameter to display normal, abnormal – not clinically significant, abnormal – clinically significant, and not done. The shift tables will present baseline and last observation post-baseline value, as applicable for each parameter.

#### **4.2.9.4 Physical examination**

Any new finding(s) or aggravated existing finding(s), judged as clinically significant by the Investigator will be reported as AEs.

#### **4.2.9.5 Vital signs**

Descriptive statistics and change from baseline for vital signs data will be presented for each treatment group by visit. Baseline to maximum post-baseline and baseline to minimum post-baseline value shift tables may be generated as applicable for each parameter and will include patients with both baseline and post-baseline data.

The normal reference ranges listed on [Table 2](#) will be used for the identification of low, normal, and high values.

#### **4.2.10 Pharmacokinetic analyses**

The PK analyses will be performed at or under the guidance of AstraZeneca Research and Development.

Benralizumab serum concentrations and derived PK parameters will be summarized using descriptive statistics at each visit. In addition to the standard statistics, geometric mean and coefficient of variation (CV%) based on log-transformation will be presented for PK data. For the computation of geometric means, arithmetic means and medians, the BLQ data are set to LLOQ/2 before computation.

For non-compartment analysis (NCA), only patients with at least three evaluable serum PK observations post first dose (collected on day 3, day 7 and either day 14 or pre-dose on day 28) will be included.

When PK concentration data is missing on scheduled visit, data from unscheduled visits will be included based on the adjusted analysis defined visit window in Section 2.2.2; on dosing visits (ie, Baseline, Days 28 and 56), pre-dose values only are included. For subjects who prematurely discontinued study drug, PK data collected after the last dose date + 28 days (one dosing cycle) +3 days (visit window) will be excluded from PK analysis.

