3.9.1.2 Other restrictions

- (a) Fertile and sexually active patients or their partners should use effective contraceptive methods throughout the study and at least for 16 weeks (5 half-lives) after last administration of the IP. Male patients should refrain from fathering child or donating sperm from the time of informed consent, and for 16 weeks (5 half-lives) after last dose of IP (see Inclusion criterion 10)
- (b) Patients must abstain from donating blood and plasma from the time of informed consent, and for 16 weeks (5 half-lives) after last dose of IP.
- (c) Patients should avoid engaging in strenuous exertion for at least 30 minutes prior to all lung function assessments at the center.
- (d) Patients should avoid eating a large meal for at least 2 hours prior to all lung function assessments at the center.

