3.10.1 Procedures for discontinuation of a subject from investigational product

At any time, subjects are free to discontinue investigational product or withdraw from the study (ie, investigational product and assessments – see Section 3.11), without prejudice to further treatment. A subject that decides to discontinue investigational should always be asked about the reason(s) and the presence of any adverse events.

All patients must be administered the first dose of IP. If the patient misses the first IP administration they must be discontinued from the study and should return for IPD visit. If the patient receives the first IP administration but misses both the 2nd and the 3rd dose they must be discontinued from the study and should return for the IPD visit. If the patient receives the first IP administration but misses either the 2nd or 3rd dose they need not discontinue from the study

All patients who prematurely discontinue investigational product should return to the study center and complete the procedures described for the premature IP Discontinuation (IPD) visit within 4 weeks \pm 3 days after the last dose of IP. At that visit, although no longer on IP, patients should be encouraged to remain in the study to complete all subsequent study visits, procedures, and assessments. Note that in this case, the IPD visit replaces the nearest regular visit while the following visits continue as possible

If the patient is not willing to participate further in the study after the IPD visit, the patient should still return for a follow up visit 8 weeks \pm 3 days after the last dose of IP for final study-related assessments.

The reasons for premature discontinuation of IP should be recorded in the eCRF.

¹ Patient is considered lost to follow up when any of the following attempts of contact are failed: 3 attempts of either phone calls, faxes or emails; having sent 1 registered letter/certified mail; or 1 unsuccessful effort to check the vital status of the patient using publicly available sources, if allowed by local regulations.

If a subject is withdrawn from study, see Section 3.11.

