5.3.4 Pharmacokinetics

5.3.4.1 Collection of samples

For the PK analysis it is important that the date and time of each SC injection is recorded for each patient.

Instructions for sample collection, processing, storage, and shipment can be found in the separate laboratory manual provided to the centers.

Serum will be collected every visit from Visit 4 to Visit 10. On the dosing days, ie, Visit 4, 8 and 9, the serum will be collected as pre-dose.

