### **3.6 Pharmacokinetic variables**

Pharmacokinetic trough concentration will be assayed for each visit where serum samples are collected.

In addition, estimation of PK parameters, ie,  $C_{max}$ ,  $t_{max}$ , and  $AUC_{[0,28d]}$  will be computed for the first dosing cycle using a noncompartmental estimation method.  $C_{max}$  and  $T_{max}$  are direct measurements of the maximum observed concentration and the time to reach the  $C_{max}$ , respectively, during the first dosing cycle.

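### The 31-day PK exclusion misses the Day 56 sample after a skipped second dose, and the NCA entry rule admits AUC(0-28d) profiles that end at Day 14

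*SAP*

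**What the plan says.** SAP 3.6 names Cmax, tmax and AUC(0-28d), which "will be computed for the first dosing cycle using a noncompartmental estimation method". Of the visit concentrations it says: "Pharmacokinetic trough concentration will be assayed for each visit where serum samples are collected". Protocol 5.3.4.1 sets the sampling: "Serum will be collected every visit from Visit 4 to Visit 10", that is Days 0, 3, 7, 14, 28, 56 and 84, with pre-dose draws on the three dosing days.

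SAP 4.2.10 then sets two rules.

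- **Entry to non-compartmental analysis (NCA):** "only patients with at least three evaluable serum PK observations post first dose", these being "collected on day 3, day 7 and either day 14 or pre-dose on day 28".
- **Late samples:** "For subjects who prematurely discontinued study drug, PK data collected after the last dose date + 28 days (one dosing cycle", with three further days for the visit window, are dropped from PK analysis.

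Protocol 3.10.1 provides that a patient who has had the first dose but "misses either the 2nd or 3rd dose they need not discontinue from the study". The SAP's own missed-dose discontinuation criterion (footnote to the withdrawal-reason table in Appendix 8.1) needs two consecutive missed doses or more than two in all, so one missed dose does not meet it.

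**The concern.** The late-sample rule shows that the sponsor wants visit concentrations to reflect one dosing cycle. It is tied to discontinuation status, however, and not to the time since the last injection. A patient who skips dose 2 and receives dose 3 has not discontinued, so a concentration two cycles after dosing is averaged with one-cycle troughs. Such values lower the Day 56 summary and widen its spread for a reason that has nothing to do with the drug's kinetics under the planned schedule.

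The NCA rule treats Day 14 and Day 28 as interchangeable. For Cmax and tmax that may be acceptable. For AUC(0-28d) it is not, because a Day 3/7/14 profile stops halfway through the interval. The SAP does not say whether AUC is then extrapolated or set to missing, so the analyst must choose after the data are in.

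**Working it through.** The documents give no figure of their own to reproduce here. The check has three parts.

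**1. Which profiles enter the NCA.** Testing every subset of {3, 7, 14, 28} against the rule leaves three: {3, 7, 14}, {3, 7, 28} and {3, 7, 14, 28}. The first ends at Day 14, leaving 14 of 28 days unsampled.

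**2. Which samples the 31-day rule catches.** The limit is 28 + 3 = 31 days.

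| Case | Doses given | Sample | Days since last dose before sample | Cut-off if coded as discontinued | Outcome |
|---|---|---|---|---|---|
| Dose 2 skipped | Days 0, 56 | Day 56 pre-dose | 56 | 56 + 31 = Day 87 | Kept whatever the coding |
| Dose 3 skipped | Days 0, 28 | Day 84 | 84 − 28 = 56 | 28 + 31 = Day 59 | Dropped if coded as discontinued, kept if not |

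**3. Size, by illustration.** Protocol 3.9.1.2 equates 16 weeks with five half-lives ("at least for 16 weeks (5 half-lives) after last administration of the IP"), so the half-life is 112 / 5 = 22.4 days. I assume one compartment with first-order absorption, C(t) ∝ [ka/(ka − k)] × (e^(−kt) − e^(−ka·t)), k = ln 2 / 22.4, ka = 0.2 to 0.6 per day. Both the model and ka are assumptions.

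*Troughs.* By 28 days absorption is nearly over, so each further cycle multiplies the concentration by about r = 2^(−28/22.4) = 0.420.

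- Day 56, dose 2 skipped, relative to schedule: C(56) / [C(28) + C(56)] ≈ r/(1 + r) = 0.420/1.420 = 0.30.
- Day 84, dose 3 skipped: (r + r²)/(1 + r + r²) = 0.597/1.597 = 0.37.
- At an assumed half-life of 15 days, r = 0.274, and the ratios are 0.22 and 0.26.
- Over half-lives of 10 to 22.4 days and absorption half-lives of 1 to 5 days, they run from 0.13 to 0.31 and from 0.14 to 0.39.

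The documents do not say how many patients skip dose 2. If 5% did (assumed), the Day 56 geometric mean would be multiplied by 0.30^0.05 = 0.94, a fall of about 6%. At 2% the factor is 0.98, and at 10% it is 0.89.

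*AUC at a half-life of 22.4 days.* Percentages are of the true AUC(0-28d). The trapezoids are linear and start from zero at Day 0.

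| ka per day | Share in Days 14-28 | {3,7,14}, cut at Day 14 | {3,7,14}, extended on the Day 7-14 slope | {3,7,28} |
|---|---|---|---|---|
| 0.6 | 43% | 54% | 98% | 99% |
| 0.35 | 46% | 51% | 102% | 97% |
| 0.2 | 52% | 47% | 110%, but the slope is upward | 92% |

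At ka = 0.2 the modelled peak is at about Day 11, so concentration is still rising between Days 7 and 14 and there is no terminal slope to use. At a half-life of 15 days the Days 14-28 share is 38-48%.

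**The case against.** The strongest reply is that SAP 4.2.10 sets only a minimum for entering the NCA. It nowhere says that AUC is cut at Day 14, and cutting it there would contradict the parameter named in SAP 3.6. That stands. A reader might infer that the reported AUC is about half its true value, or that the named parameters are not what will be reported. The documents do not support either reading. Extending a falling Day 7-14 slope recovers 98-102% of the area in noise-free data, and Cmax and tmax are observed values whose definition is unchanged. What remains is that a two-point slope is imprecise in one patient, may not exist at all, and is covered by no stated rule.

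Second, the PK analysis set (Protocol 8.3.5, SAP 2.1.5) requires samples assumed to be unaffected by factors such as protocol violations. That could remove skipped-dose values, but it is discretionary and does not name missed doses. A single skip that Protocol 3.10.1 tolerates is not plainly a violation.

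Third, Protocol 3.10.1 speaks of not leaving the study, which differs from not discontinuing the product. Dose 3 is the last scheduled dose, so a patient who skips it may well be coded as a discontinuer, and the existing rule then removes the Day 84 value. This limits the certain gap to Day 56.

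Fourth, some missing Day 28 values are already covered. Unscheduled samples may fill the analysis window, and a patient who stops after dose 1 has a discontinuation visit about four weeks after that dose.

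A reader might also cite the absence of missed doses from SAP 8.3. That list covers only deviations bearing on the primary endpoint, so it says nothing about PK handling.

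**Conclusion.** The rules are wrong as written, but the matter is minor and confined to descriptive PK.

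The firm finding is the Day 56 value after a skipped dose 2. As written, the 31-day sentence cannot exclude it, and it sits at roughly 0.30 of the scheduled trough (0.22 at an assumed 15-day half-life). The Day 84 finding is conditional on coding. For AUC(0-28d), the rule admits profiles in which about 43-52% of the area is unsampled, so the value must rest on at most a two-point slope or cannot be estimated.

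The date arithmetic and the list of admitted profiles come from the documents alone. The ratios and shares rest on the assumed PK model. How many patients fall in either group is unknown.

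A reader might go on to infer that both rules bias exposure downward, that accumulation will look weaker, or that all the PK results are affected. The downward pull is shown only for the skipped-dose troughs, and the direction for AUC is not established. Neither document plans an accumulation analysis. Cmax, tmax and the Day 3, 7 and 14 concentrations are also reported. No efficacy conclusion or sample size depends on any of this.

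**What to change.** Make two changes in SAP 4.2.10.

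1. Apply the existing 28 + 3 day limit to every patient, counted from the last dose actually given before the sample and regardless of discontinuation status. List the excluded values separately.
2. Report AUC(0-28d) only for patients with a Day 28 pre-dose sample, or an in-window unscheduled sample taken before dose 2. Set it to missing otherwise. Keep Day 3/7/14 profiles for Cmax and tmax.

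The cost is two sentences and a slightly smaller n for AUC and the late trough summaries. One detail needs care. Visit 10 has a window of ±7 days, so a literal 31-day limit would also drop an in-window Day 84 sample from a fully dosed patient (dose on Day 56, visit on Day 91: 35 days). If that loss is unwanted, the limit can carry the window of the visit concerned, or the exclusion can be keyed to whether the immediately preceding scheduled dose was given.

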#### **4.2.11 Immunogenicity analyses**

Anti-drug antibody assessments will be conducted and analyzed as per the details in Section 3 of the “Statistical Analysis Plan for Benralizumab Anti-Drug Antibody data” with the following exceptions:

- Demographics/patient characteristics summary by ADA status and further by positive subgroup will not be produced.
- Summaries will not be produced by baseline blood eosinophils count cut off ( $\geq 300$  or  $< 300$  cells/ $\mu\text{L}$ ) due to all patients enrolled in this study having baseline blood eosinophils count  $\geq 300$  cells/ $\mu\text{L}$ .
- Summary of first positive post-baseline ADA response during the study will not be produced.
- Listing of patients who had ADA titres increased by  $>4$ -fold from onset to maximum titre will not be produced.
- Eosinophil levels will be summarized by visit for ADA positive and negative patients only.
- Summary of nAb will not be provided by subgroup of ADA positive.
- Relationship between ADA and efficacy will not be explored.
- Relative risk tables for select safety outcomes will be omitted due to low frequency of events.
- Listing of ADA titre by visit for ADA-positive patients will be produced.

## 5. INTERIM ANALYSES

No interim analysis is planned for this study.

## 6. CHANGES OF ANALYSIS FROM PROTOCOL

Protocol Section 8.5.2.3 mentions that ECG intervals will be summarized by presenting summary statistics of observed and change from baseline values. The (uncorrected) QT interval will be corrected according to the Fridericia's formula. However, this study collects only ECG outcome of the overall evaluation recorded as normal and abnormal; therefore, the summaries of observed and change from baseline values will not be performed.

## **8. APPENDIX**

### **8.1 Accounting for missing data for pre-bronchodilator FEV1**

Patients dropping out of this study may lead to unobserved data. It is hoped the amount of missing data is minimized in this study as patients are encouraged to complete visits until they withdraw from the study.

This section summarizes how we will describe the pattern of and reasons for missing data from the study. It will also describe how we plan to account for missing data, including both the primary and sensitivity analyses to assess the robustness of the treatment effect under different underlying assumptions to account for missing data.

#### *Missing data descriptions*

Tabular summaries for the percentage of patients by the reason for discontinuation of randomized treatment as well as for withdrawal from the study will be presented by treatment to describe why patients discontinue from randomized treatment or withdraw from the study. The time to discontinuation of randomized treatment and withdrawal from the study will be presented using Kaplan Meier plots (overall and split by treatment related/not treatment

related reason for discontinuation, as defined in Tables 1 and 2). Dependent on these outputs additional exploratory analyses may be produced as deemed necessary to further understand the pattern of missing data.

Primary analysis under the Treatment Policy Estimand using the Missing at Random assumption

The primary analysis of the pre-BD FEV1 is under the treatment policy estimand which allows for differences in outcomes over the entire study treatment period to reflect the effect of initially assigned randomized treatment as well as if subsequent treatments are taken. This primary analysis includes all data until patients withdraw from the study regardless of if they discontinue from randomised treatment. The Mixed Model Repeated Measures model (MMRM) used is a direct likelihood approach (DL) which is valid under the Missing at Random (MAR) assumption.

Sensitivity analysis under the Treatment Policy Estimand using both MAR and MNAR assumptions

To examine the sensitivity of the results of the primary analysis to departures from the underlying assumptions, sensitivity analyses of the repeated measures analyses will be performed for the pre-BD FEV1 using controlled sequential multiple imputation methods based on pattern mixture models, as described in the European Medicines Agency Guideline on Missing Data in Confirmatory Clinical Trials ([EMA 2010](#)). As with the primary analysis, the sensitivity analyses include all data until patients withdrew from the study regardless of if patients discontinue from randomised treatment.

The imputation process consists of a sequence of multiple imputation (MI) steps, where each step is intended to impute missing values at 1 timepoint only. This model will assume that some pre-specified subset of patients who withdraw from the study have correlations with future (unobserved) visits similar to patients in the placebo arm. This allows us to assess various deviations from the MAR assumption.

The assumptions that will be used to impute the missing data who withdraw early are as follows:

- (a) MAR: Assumes that the trajectory for patients who dropped out in each arm is similar to those observed in their own treatment arm
- (b) DRMI: Assumes that the trajectory for patients in the benralizumab arms who dropped out for a treatment related reasons (according to the classification for DRMI) is similar to that of the placebo patients, whereas the remaining patients who has dropped out are imputed assuming MAR.

Approach b) can be considered more conservative than the approach for the primary analysis because the assumptions mean that as soon as patients withdraw for a treatment related reason, they begin to worsen immediately.

The MNAR imputation is achieved by using only appropriate data at each stage of the imputation. Imputation will be done in 2 steps, the non-monotone (intermediate) missing FEV1 values will be imputed first (Markov chain Monte Carlo [MCMC] method is used to partially impute the data using SAS PROC MI) and then the missing value at each visit will be imputed using a sequential regression method (using MONOTONE REG option of SAS PROC MI).

For example, to impute missing values at time  $t$  for patients in the benralizumab arms who dropped out due to an AE, include only placebo observations up to and including time  $t$ , plus observations from patients in the benralizumab arms, that dropped out due to an AE, up to and including time  $t-1$ . This is carried out for each visit, 1 at a time using observed data, and missing values imputed up until that visit. Placebo missing observations and benralizumab observations that are not missing due to AEs are imputed assuming missing at random (MAR) and follow the pattern of observed placebo observations in each treatment arm, respectively. One-hundred imputations will be carried out. A seed of 784088 will be used for the monotone imputation step and a seed of 409345 will be used for the sequential regression imputation step. The analysis of each imputed dataset will be as described for the primary analysis in Section 4.2.5.1 and these will be combined using SAS procedure PROC MIANALYZE.

To avoid possible convergence issues when fitting MMRM models to 100 imputed datasets, the estimated unstructured covariance parameters from the first imputation where the model converges will be used as the starting values to fit the models for all imputed datasets.

A summary of reasons for patients withdrawing from the benralizumab treatment arm and the corresponding treatment arm used to calculate the imputation under MAR, and DRMI is given in Table 1.

Reason for withdrawal	MAR	DRMI
Adverse Event	Benralizumab	Placebo
Development of study-specific discontinuation criteria*	Benralizumab	Placebo
Death	Benralizumab	Placebo
Severe non-compliance to protocol	Benralizumab	Placebo
Eligibility criteria not fulfilled	Benralizumab	Benralizumab
Patient lost to follow up	Benralizumab	Benralizumab
Patient decision	Benralizumab	Based on review prior to study unblinding
Other	Benralizumab	Based on review prior to study unblinding

\*Development of study-specific discontinuation criteria are based on the following: anaphylactic reaction to the IP requiring administration of epinephrine, development of helminth parasitic infestations requiring hospitalization, 2 consecutive doses of IP missed or more than 2 scheduled doses of IP are missed during course of the study, an asthma-related event requiring mechanical ventilation.

Together with the primary analysis, the sensitivity analyses are considered to cover the range from realistic to plausible worst case assumptions about missing data. The MAR multiple imputation approach is expected to correspond closely to the primary analysis, and is included to allow for comparisons with MNAR assumptions (specifically methods b) using the same multiple imputation methodology.

The dropout reason-based multiple imputation (DRMI) approach was selected as the most conservative approach based on the fact that placebo patients are receiving standard of care and are not expected to change to a substantially more effective treatment after withdrawing from study or study treatment. For patients receiving benralizumab who withdraw from the study due to treatment related reasons, it is assumed that, at worst, they would be on the standard of care treatment, ie, the placebo arm. For patients receiving benralizumab who withdraw from the study due to non-treatment related reasons, it seems reasonable to assume they would be similar to those patients who complete treatment.

